6.3 Missing Data Imputation

Missing Data Imputation for SVR

HCV RNA values will be selected for analysis based on the analysis windows defined in Section 6.2.

For analyses of SVR, subjects missing visit values will have backward imputation applied, if possible. For backward imputation, if the nearest HCV RNA value after the SVR window is unquantifiable or undetectable, then it will be used to impute the HCV RNA value in the SVR window. If a subject is missing an HCV RNA value within the appropriate SVR window after performing backward imputation, then this value will be imputed with an HCV RNA value from a local laboratory if present; otherwise, the HCV RNA value will be missing. Subjects with missing HCV RNA data in the analysis window, after imputations, will be imputed as a failure.

Regardless of the imputation method described above, if a subject starts another treatment for HCV, then all HCV RNA values for this subject measured on or after the start date of the new HCV treatment will be excluded from analyses. The subject will be considered a failure for summaries of viral response at all time points after the start of the new HCV treatment.

Missing Data Imputation for Virologic Failure

If HCV RNA values from the central laboratory are missing but a local laboratory value is present in the appropriate time period, then the local laboratory value will be used to assess post-treatment relapse and on-treatment virologic failure.

Missing Data Imputation for PRO Questionnaires

If a respondent answers at least 50% of the items in a multi-item scale of the SF-36v2, the missing items will be imputed with the average score of the answered items in the same scale. In cases where the respondent did not answer at least 50% of the items, the score

for that domain will be considered missing. The Mental and Physical Component Summary measures will not be computed if any domain is missing. For TSQM, if a respondent answers at least 2 items in the 3 item scales of Side Effects or Effectiveness, the missing items will be imputed with the average score of the answered items in the same scale. For EQ-5D-3L, health state index and VAS scores no imputation will be performed for missing items.

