At the Screening Visit and at the last Post-Treatment Study Visit, subjects with compensated cirrhosis will be required to undergo a liver ultrasound to screen for HCC, unless the subject has a historical liver ultrasound, CT scan or MRI performed for HCC screening within 3 months prior to those visits, in which case the result of the historical ultrasound, CT scan or MRI will be used as the result for the Study Visit assessment. A positive ultrasound result suspicious of HCC will be confirmed with CT scan or MRI. Alternate methods of screening for HCC (i.e., CT scan or MRI) at a study visit should be discussed with the study designated physician.

Patient Reported Outcomes (PRO) Instruments (Questionnaires)

Subjects will complete the self-administered PRO instruments on the study visits specified in [Appendix C](#) and [Appendix D](#). Subjects should be instructed to follow the instructions provided with each instrument and to provide the best possible response to each item. Site personnel shall not provide interpretation or assistance to subjects other than encouragement to complete the tasks. Subjects who are functionally unable to read any of the instruments may have site personnel read the questionnaires to them. Site personnel should encourage completion of each instrument at all specified visits and should ensure that a response is entered for all items.

Short Form 36 – Version 2 Health Survey (SF-36v2)

The SF-36v2 is a general Health Related Quality of Life (HRQoL) instrument with extensive use broad variety of health conditions and is the standard in literature for HCV. The SF-36v2 instrument comprises 36 total items (questions) targeting a subject's functional health and well-being in 8 domains (physical functioning, role physical, bodily pain, general health, vitality, social functioning, role emotional and mental health). Domain scores are also aggregated into a Physical Component Summary score and a Mental Component Summary score. Higher SF-36v2 scores indicate a better state of health. The SF-36v2 should require approximately 10 minutes to complete.

Treatment Satisfaction Questionnaire-Medicine (TSQM)

The TSQM is a 14-item instrument and includes assessments of satisfaction with a medication's effectiveness (Effectiveness, three items), lack of side effects (Side Effects; five items), convenience (three items) and the subject's global satisfaction (Global Satisfaction; three items).

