10.5.1 Imputation Approaches

No imputation methods will be employed other than those described in Section 6.3.

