10.9 Patient Reported Outcomes

The SF-36v2 is a general Health Related Quality of Life (HRQoL) instrument with extensive use in a broad variety of health conditions and is the standard in literature for HCV. The SF-36v2 instrument comprises 36 total items (questions) targeting a subject's functional health and well-being in 8 domains (physical functioning, role physical, bodily pain, general health, vitality, social functioning, role emotional and mental health). Domain scores are also aggregated into a Physical Component Summary score and a Mental Component Summary score. Higher SF-36v2 scores indicate a better state of health.

The TSQM is a 14-item instrument and includes assessments of satisfaction with a medication's effectiveness (Effectiveness, three items), lack of side effects (Side Effects; five items), convenience (three items) and the subject's global satisfaction (Global Satisfaction; three items). TSQM scores range from 0 – 100 with higher scores indicating better satisfaction.

The EQ-5D-3L is a health state utility instrument that evaluates preference for health status (utility). The 5 items in the EQ-5D-3L comprise 5 dimensions (mobility, self-care, usual activities, pain/discomfort, and anxiety/depression) each of which are rated on 3 levels of severity. Responses to the 5 items encode a discrete health state which is mapped to a preference (utility) specific for different societies. Subjects also rate their perception of their overall health on a separate visual analogue scale (VAS).

The mean change from baseline to each applicable post-baseline timepoint in the SF-36v2 Mental Component Summary (SF-36-MCS) and Physical Component Summary (SF-36-PCS) scores; EQ5D-3L health state index and VAS score will be summarized descriptively at each applicable visit and for change from baseline to each applicable visit.

The following analyses of patient reported outcomes (PROs) also will be performed:

- Number and percentage of subjects who have ever experienced an increase from baseline up through each applicable timepoint of greater than or equal to 1/2 standard deviation (SD) at baseline points in the SF-36 MCS, PCS and SF-36 domain scores^{2,3}

TSQM Effectiveness, Side Effects, Convenience, and Global Satisfaction scores will be summarized descriptively at each applicable visit.

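### The TSQM missing-item rule counts the five-item Side Effects scale as a three-item scale and gives no rule for two of the real three-item scales

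*SAP*

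**What the plan says.** The missing-item rule is in the PRO part of SAP 6.3: "For TSQM, if a respondent answers at least 2 items in the 3 item scales of Side Effects or Effectiveness". When that condition is met, missing items take the mean of the answered items in the scale. Protocol 8.1.3 has the same sentence.

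SAP 10.9 describes the instrument: "The TSQM is a 14-item instrument", made up of "satisfaction with a medication's effectiveness (Effectiveness, three items") and "lack of side effects (Side Effects; five items), convenience (three items) and the subject's global satisfaction (Global Satisfaction; three items"). Protocol 5.3.1.1 gives matching counts: "effectiveness (Effectiveness, three items), lack of side effects (Side Effects; five items), convenience (three items").

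All four scales are reported: "TSQM Effectiveness, Side Effects, Convenience, and Global Satisfaction scores will be summarized descriptively at each applicable visit" (SAP 10.9).

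For PRO imputation in general, SAP 10.1 refers to Sections 6.3 and 10.9. Section 10.9 adds no missing-item rule for the TSQM.

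**The concern.** The rule is meant to direct scoring, and it disagrees with the description of the instrument in the same SAP. There are three gaps.

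- **Side Effects.** The condition is written for a three-item scale but applied to a five-item one. One programmer may accept two of five answers. Another may decide that the condition cannot apply to a five-item scale and impute nothing.
- **Convenience and Global Satisfaction.** They have as many items as Effectiveness but are not named. A form with one item blank yields an Effectiveness score but no score on either of these scales, and no reason is given.
- **Missing scores.** For SF-36v2, SAP 6.3 says that a domain is missing when too few items are answered. It has no such sentence for any TSQM scale.

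At stake are the number of scores behind each TSQM summary and the way some Side Effects scores are derived. The study is open-label, so a scoring choice made after the data have been seen would be post hoc.

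**Working it through.** **1. Item count.** Effectiveness 3 + Side Effects 5 + Convenience 3 + Global Satisfaction 3 = 14, the total stated in SAP 10.9. With three Side Effects items the sum would be 12. The documents alone show that five is the consistent count, so the error lies in the imputation sentence.

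**2. What two answers mean.** On a three-item scale, 2/3 = 66.7% answered and at most one item imputed. On Side Effects, 2/5 = 40% answered and up to three imputed. The same paragraph of SAP 6.3 asks for at least 50% on SF-36v2 scales; on five items that is 0.5 × 5 = 2.5, so three answers.

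**3. Assumptions for size.** The documents give neither a rate of missing items nor the correct Side Effects minimum. I assume independent, equal per-item missingness q of 2%, 5% and 10%, and a correct minimum of either 3 or 4. Planned forms number about 200: 100 subjects, at end of treatment and Post-Treatment Week 12 (the TSQM is not given on Day 1).

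**4. Side Effects forms scored under the literal reading that should not be.**
- Exactly 2 of 5 answered: 10(1−q)²q³.
- Exactly 3 of 5 answered: 10(1−q)³q².
- If the minimum is 3, only the first group is wrongly scored. If it is 4, both groups are.

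| q | 2 of 5 | 3 of 5 | Wrongly scored, minimum 3 | Wrongly scored, minimum 4 |
|---|---|---|---|---|
| 2% | 0.008% | 0.38% | 0.008% (0.02 of 200 forms) | 0.38% (0.8 of 200) |
| 5% | 0.11% | 2.14% | 0.11% (0.2 of 200) | 2.26% (4.5 of 200) |
| 10% | 0.81% | 7.29% | 0.81% (1.6 of 200) | 8.10% (16.2 of 200) |

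**5. Convenience and Global Satisfaction, each.**
- Complete forms: (1−q)³.
- Forms with exactly one of three missing: 3q(1−q)². These are the forms that the Effectiveness rule would rescue.

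| q | Scores per 100 forms, no imputation | Scores per 100 forms, 2-of-3 rule | Lost per 100 forms |
|---|---|---|---|
| 2% | 94.1 | 99.9 | 5.8 |
| 5% | 85.7 | 99.3 | 13.5 |
| 10% | 72.9 | 97.2 | 24.3 |

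**The case against.** **The two unnamed scales are already settled.** SAP 10.1 sends PRO imputation to Sections 6.3 and 10.9, and neither names Convenience or Global Satisfaction, so they are not imputed. This stands. SAP 10.5.1 points the same way ("No imputation methods will be employed other than those described in Section 6.3"), but it sits under the SVR sensitivity analyses and is weaker support. Two things remain: scales of equal length are treated differently without a reason, and nothing says that the unimputed score is then missing.

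**The omission may be deliberate.** A reader might infer that leaving these scales out was a slip and that two of three is certainly right for them. The documents do not show that. The 2-of-3 rule is an analogy with Effectiveness, and the TSQM scoring instructions are not among the documents.

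**There is no firm 2-of-5 rule.** A reader might infer that the plan definitely scores Side Effects from two answers. The text does not go so far. Its condition is stated for three-item scales, so on a five-item scale it is contradictory; two of five is only the literal reading.

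**Few forms should be incomplete.** Protocol 5.3.1.1 says that site staff "should ensure that a response is entered for all items". This makes the upper assumed rates unlikely. It reduces the size of the problem but leaves the contradiction in place.

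**Conclusion.** The point holds, as a minor one. The TSQM sentence in SAP 6.3 and Protocol 8.1.3 is wrong on the documents' own item counts. Two reported three-item scales lack the imputation given to the third, and no passage defines a missing TSQM score.

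For Side Effects the size depends on the unknown minimum: close to nil if it is three answers, up to about 8% of forms if it is four and a tenth of items are missing. For Convenience and Global Satisfaction the loss is about 6, 14 or 24 scores per 100 forms at the three assumed rates. All these figures rest on independent, equal item missingness, which the documents do not give.

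A reader might infer that the trial's conclusions are at risk. They are not: TSQM scores are summarized descriptively only, and no primary or secondary endpoint depends on them. A reader might also infer that only the number of scores changes. That is assured only if items are missing completely at random; otherwise the means of the scored forms can shift as well.

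**What to change.** Rewrite the TSQM sentence in SAP 6.3:

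- Treat Side Effects as a five-item scale with its own minimum, taken from the TSQM scoring instructions.
- Name Effectiveness, Convenience and Global Satisfaction as the three-item scales and give them one common rule: two of three, as already stated for Effectiveness, unless the scoring instructions say otherwise.
- Cite those instructions for all four scales.
- State that a scale score is missing when its minimum is not met.

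Record the change in SAP 12.1, which now lists only the removal of the HIV co-infection analyses, and reconcile Protocol 8.1.3 with the item counts in Protocol 5.3.1.1. The cost is a few sentences in SAP 6.3, one line in SAP 12.1, the matching protocol correction and a small edit to the scoring program. No new data are needed.

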7.0 Demographics, Baseline Characteristics, Medical History, and Other Medications

The ITT population will be used to summarize demographics, baseline characteristics, medical history and previous, concomitant, and post-treatment medications; data will be summarized across all subjects and by assigned treatment arm.

7.1 Demographic and Baseline Characteristics

Categorical demographic and baseline characteristic variables will be summarized with the number and percentage of subjects in each category. Continuous variables will be summarized with descriptive statistics (number of non-missing observations, mean, standard deviation, median, maximum and minimum). For categorical variables, the number of missing observations will be displayed, if applicable, on the summary tables. Percentages will be calculated based on the number of non-missing observations.

Continuous demographic and baseline characteristics include age, weight, height, body mass index (BMI), baseline log₁₀ HCV RNA level, creatinine clearance (Cockcroft-Gault calculation), eGFR (using the modification of diet in renal disease [MDRD] formula), platelet count, albumin, GGT, APRI, FIB-4, AST, ALT, and total, direct and indirect bilirubin.

Categorical demographic and baseline characteristics include:

- Age (< 65 or ≥ 65 years) and (< 75 or ≥ 75 years);
- Sex (male or female);

- Race (White, Black/African-American, Asian, American Indian or Alaska Native, or Native Hawaiian or Other Pacific Islander) and black race (black or non-black);
- Ethnicity (Hispanic or Latino, Not Hispanic or Latino);
- Baseline BMI (< 30 or ≥ 30 kg/m²);
- HCV genotype and subtype (using central laboratory results and final genotype/subtype results, see Section 10.8);
- Cirrhosis status (yes/no);
- Chronic Kidney Disease stage (Stage 1, 2, 3, 4, or 5);
- Baseline HCV RNA level ($< 1,000,000$; $\geq 1,000,000$ to $< 2,000,000$; or $\geq 2,000,000$ IU/mL);
- Baseline platelet count (< 90 or $\geq 90 \times 10^9/L$);
- Baseline albumin (< 35 or ≥ 35 g/L);
- Baseline eGFR (< 15 , ≥ 15 to < 30 , ≥ 30 to < 45 , ≥ 45 to < 60 , or ≥ 60 mL/min/1.73 m²);
- Baseline creatinine clearance (< 15 , ≥ 15 to < 30 , ≥ 30 to < 45 , ≥ 45 to < 60 , or ≥ 60 mL/min);
- Baseline fibrosis stage (equivalent to Metavir F0 - F1, F2, F3, or F4);
- Concomitant use of Proton Pump Inhibitors (PPIs) (yes/no);
- Tobacco use (current, former, never, or unknown);
- Alcohol use (current, former, never, or unknown);
- Injection drug use (yes, within last 12 months; yes, more than 12 months ago; or no);
- Use of stable opiate substitution (yes/no);
- History of diabetes (yes/no);
- History of depression or bipolar disorder (yes/no);
- History of bleeding disorders (yes/no);
- History of cardiovascular disease (yes/no);

In addition, for cirrhotic subjects, the following will be summarized:

- Baseline Child-Pugh score (5, 6, or > 6).

Summaries of baseline resistance are described in Section 10.8.

Any concomitant medication coded to the WHO Drug Dictionary ATC code of A02BC will be counted as a PPI.

Baseline CKD categorization is defined according to eGFR as shown in Table 4 below:

Table 4. Definition of Chronic Kidney Disease Stages

CKD Stage	eGFR (mL/min/1.73 m ²)*
1	≥ 90
2	60 to < 90
3	30 to < 60
4	15 to < 30
5	< 15 or requiring dialysis

* $eGFR (mL/min/1.73 m^2) = 175 \times (\text{Serum Creatinine})^{-1.154} \times \text{Age}^{-0.203} \times (0.742 \text{ if female}) \times (1.21 \text{ if black})$.

Subjects will be determined to be requiring dialysis based on the Medical History (MH) eCRF. Requiring dialysis is defined as having medical history coded with any of the Preferred Terms or Lowest Level Terms specified Table 5.

Table 5. Dialysis Related Preferred Terms and Lowest Level Terms

Category	Preferred Term	Lowest Level Term
Dialysis	Artificial kidney device user	Haemodialysis fistula thrombosis
	Dialysis	Dialysis access malfunction
	Dialysis device insertion	Dialysis induced hypertension
	Haemodialysis	Hypotension during dialysis
	Haemofiltration	Thrombosis prophylaxis in hemodialysis
	Peritoneal dialysis	Dialysis device complication
	Renal replacement therapy	Dialysis dementia
	Bloody peritoneal effluent	Dialysis efficacy test
	Dialysis amyloidosis	Dependence on renal dialysis
	Dialysis disequilibrium syndrome	Artificial kidney clotting during dialysis
	Dialysis membrane reaction	Blood leak in dialyser
	Dialysis related complication	
	Extensive interdialytic weight gain	
	Haemodialysis complication	
	Haemodialysis-induced symptom	
	Inadequate haemodialysis	
	Intradialytic parenteral nutrition	
	Peritoneal cloudy effluent	
	Peritoneal dialysis complication	
	Peritoneal effluent abnormal	
	Peritoneal effluent erythrocyte count increased	
	Peritoneal effluent leukocyte count increased	
	Ultrafiltration failure	

Baseline fibrosis stage is defined for subjects with non-missing liver biopsy scores, FibroScan scores, or FibroTest scores. Only one score will be used to categorize each subject even if a subject has more than one score recorded. If a biopsy score is present, then it will be used to categorize the subject, regardless of the FibroScan/FibroTest score. Similarly, if a FibroScan score is present along with a FibroTest score, then the FibroScan score will be used to categorize the subject. If biopsy and FibroScan scores are not

present and more than one FibroTest result is available, then the baseline FibroTest result (i.e., last non-missing FibroTest result on or before Day 1) will be used to categorize the subject. Subjects will be categorized as F0 – F1, F2, F3 or F4 according to [Table 6](#).

Table 6. Baseline Fibrosis Stage

Baseline Fibrosis Stage, Metavir Equivalent	Liver Biopsy Metavir, Batts Ludwig, Knodell, IASL, Scheuer, or Laennec Score	Liver Biopsy Ishak Score	FibroScan (kPa)	FibroTest*
F0 – F1	0 or 1	0, 1, or 2	< 8.8	≤ 0.48
F2	2	3	≥ 8.8 to < 9.6	0.49 to 0.58
F3	3	4	≥ 9.6 to < 12.5	0.59 to 0.72
F4	4	≥ 5	≥ 12.5	≥ 0.73

* APRI will not be used to derive baseline Fibrosis Stage. However, per inclusion/exclusion criteria, subjects need to have concordant FibroTest and APRI scores in order to determine eligibility.

Presence or absence of cirrhosis will be determined as collected in EDC which includes the instructions, "Please indicate the subject's Metavir system fibrosis score" – "F2 - F3" is considered as non-cirrhotic and "F4" is considered cirrhotic."

The central laboratory calculates the estimated creatinine clearance (CrCl) based on the following Cockcroft-Gault formula:

$$\text{CrCl (mL/min)} = [(140 - \text{age}) \times (\text{weight in kg}) \times (0.85 \text{ if female})] / [\text{serum creatinine (mg/dL)} \times 72].$$

The central laboratory calculates the eGFR by MDRD based on the following formula:

$$\text{eGFR (mL/min/1.73 m}^2\text{)} = 175 \times (\text{Serum Creatinine})^{-1.154} \times (\text{Age})^{-0.203} \times (0.742 \text{ if female}) \times (1.212 \text{ if African American}).$$

Baseline APRI and FIB-4 are calculated by the equations below. Subjects who do not have concurrent AST and platelet values at baseline will be excluded from the summary of baseline APRI. Age is defined in years at baseline. Subjects who do not have

concurrent values of AST, ALT and platelet count at baseline or subjects who are missing age will be excluded from the summary of FIB-4.

$$\text{APRI} = \frac{\frac{\text{AST Level (U/L)}}{\text{AST (Upper Limit of Normal)(U/L)}}}{\text{Platelet Count (10}^9\text{/L)}} \times 100$$

$$\text{FIB-4} = \frac{\text{Age (years)} \times \text{AST Level (U/L)}}{\text{Platelet Count (10}^9\text{/L)} \times \sqrt{\text{ALT (U/L)}}}$$

Baseline Child-Pugh score is determined by the Day 1 assessment of ascites and hepatic encephalopathy along with the baseline values of total bilirubin, serum albumin, and international normalized ratio (INR). The Child-Pugh score is the sum of the points assigned for each of the five observed findings as defined in [Table 7](#).

Table 7. Child-Pugh Classification of Severity of Cirrhosis

Parameter	Points Assigned for Observed Findings		
	1	2	3
Total bilirubin, µmol/L (mg/dL)	< 34.2 (< 2)	34.2 – 51.3 (2 – 3)	> 51.3 (> 3)
Serum albumin, g/L (g/dL)	> 35 (> 3.5)	28 – 35 (2.8 – 3.5)	< 28 (< 2.8)
INR	< 1.7	1.7 – 2.3	> 2.3
Ascites*	None	Slight	Moderate to severe
Hepatic encephalopathy**	None	Grade 1 or 2 (or suppressed with medication)	Grade 3 or 4 (or refractory to medication)

Child-Pugh category A: 5 – 6 points; Child-Pugh category B: 7 – 9 points; Child-Pugh category C: 10 – 15 points

* None;

Slight ascites = Ascites detectable only by ultrasound examination;

Moderate ascites = Ascites manifested by moderate symmetrical distension of the abdomen;

Severe ascites = Large or gross ascites with marked abdominal distension.

** None: normal consciousness, personality, neurological examination, electroencephalogram;

Grade 1: restless, sleep disturbed, irritable/agitated, tremor, impaired handwriting, 5 cps waves;

Grade 2: lethargic, time-disoriented, inappropriate behavior, asterixis, ataxia, slow triphasic waves;

Grade 3: somnolent, stuporous, place-disoriented, hyperactive reflexes, rigidity, slower waves;

Grade 4: unarousable coma, no personality/behavior, decerebrate, slow 2 to 3 cps delta activity.

7.2 Medical History

Medical history will be coded using the Medical Dictionary for Regulatory Activities (MedDRA). The actual version of the MedDRA coding dictionary will be noted in the clinical study report.

Medical history data will be summarized and presented by primary MedDRA System Organ Class (SOC) and Preferred Term (PT). The SOCs will be presented in alphabetical order, and the preferred terms will be presented in alphabetical order within each SOC.

The number and percentage of subjects with a particular preferred term will be summarized. Subjects reporting more than one preferred term within a SOC will be counted only once for that SOC.

Histories of diabetes, bleeding disorders, depression or bipolar disorder, and cardiovascular disease will be defined by a subject having medical history coded to at least one preferred term within any of the high level terms specified for the category in [Table 8](#).

Table 8. Medical/Surgical History eCRF

Medical History eCRF	
Category	MedDRA High Level Term Name
Diabetes	Diabetic complications cardiovascular Diabetic complications dermal Diabetic complications gastrointestinal Diabetic complications NEC Diabetic complications neurological Diabetic complications ophthalmic Diabetic complications renal Diabetes mellitus (incl subtypes) Hyperglycaemic conditions NEC
Bleeding disorders	Coagulation factor deficiencies Coagulopathies Platelet disorders NEC Thrombocytopenias Coagulation disorders congenital

Table 8. Medical/Surgical History eCRF (Continued)

Medical History eCRF	
Category	MedDRA High Level Term Name
Depression or bipolar disorder	Depressive disorders Bipolar disorders Mood alterations with manic symptoms
Cardiovascular disease	Coronary artery disorders NEC Ischaemic coronary artery disorders Cardiac conduction disorders Rate and rhythm disorders NEC Supraventricular arrhythmias Ventricular arrhythmias and cardiac arrest Congenital cardiac malpositions and transpositions Congenital cardiac structural defects NEC Congenital cardiovascular disorders NEC Cardiac disorders congenital NEC Cardiac hypoplasias congenital Cardiac malpositions congenital Cardiac septal defects congenital Cardiac valve disorders congenital Cardiovascular disorders congenital NEC Great vessel disorders congenital Multiple cardiac abnormalities congenital Persistent foetal circulation disorders Heart failure signs and symptoms Heart failures NEC Left ventricular failures Right ventricular failures Accelerated and malignant hypertension Renal hypertensions Vascular hypertensive disorders NEC Coronary necrosis and vascular insufficiency Infectious myocarditis Noninfectious myocarditis Peripheral vasoconstriction, necrosis and vascular insufficiency Aortic valvular disorders Cardiac valve disorders NEC Mitral valvular disorders Pulmonary valvular disorders Tricuspid valvular disorders Aortic inflammatory disorders Arterial inflammations Vasculitides NEC

